9.1. Adverse Events

An AE is any undesirable event that occurs to a participant during a study, whether that event is considered related to Study Drug.

All summaries of AEs will be based on treatment-emergent adverse events (TEAEs) unless specified otherwise.

An adverse event is considered a TEAE if:

- The adverse event first occurred on or after the date of the first dose of study drug; or
- The adverse event was present before the date of the first dose of study drug, but it increased in severity or became serious on or after the date of the first dose of study drug.

9.1.1. Severity of Adverse Events

The severity of each AE should be characterized and then classified into one of three clearly defined categories as follows:

- Mild
- Moderate
- Severe

These three categories are based on the Investigator's clinical judgment, which in turn depends on consideration of various factors such as the participant's report and the physician's observations.

The missing severity of an AE will be imputed to “severe”.

9.1.2. Relationship to Study Drug

The relationship of each AE to the Study Drug will be based on the Investigator's assessment as to whether there is a reasonable possibility the AE was caused by the Study Drug.

The causal relationship between an AE and the study drug will be categorized as two cases in the CRFs as follows:

Case 1: If AE started while participant was consented under protocol v 2.0, then the categories will be

- Unlikely Related,
- Possibly Related, and
- Probably Related.

The missing relationship to study drug of an AE will be imputed to “Probably Related”.

Treatment-related TEAEs are defined as the TEAEs with relationship to study drug is “Possibly Related” or “Probably Related”.

Case 2: If AE started while participant was consented under protocol v 3.0 and/or above, then the categories will be

- Not Related, and
- Reasonable Possibility.

The missing relationship to study drug of an AE will be imputed to “Reasonable Possibility”.

Treatment-related TEAEs are defined as the TEAEs with relationship to study drug is “Reasonable Possibility.”

For the analysis purposes (regardless of protocol amendment version), treatment-related TEAEs are defined as the TEAEs with relationship to study drug is “Possibly Related” or “Probably Related” or “Reasonable Possibility.”

9.1.3. Serious Adverse Events (SAEs)

A Serious Adverse Event (SAE) includes (but is not limited to) an experience occurring at any dose that results in any of the following outcomes:

- Death,
- Life-threatening,
- In-patient hospitalization,
- A persistent or significant disability/incapacity,
- A congenital anomaly/birth defect, and
- Other medically important event

The number and proportion of participants who experience the event according to MedDRA system organ class (SOC) and preferred term (PT) will be presented by treatment group. TEAEs will be further summarized, individually, by maximum severity and relationship to study drug. Adverse events related to study drug, AEs leading to withdrawal, SAEs, and deaths will be similarly summarized.

An overall summary of TEAEs will be provided by treatment. This summary will present number and percentage of participants with TEAEs per the following classifications:

- Participants with any TEAEs

- Participants with Treatment-Emergent Drug-Related AEs
- Participants with Treatment-Emergent AEs by Maximum Severity as Mild, Moderate, and Severe.
- Participants with TEAE leading to discontinuation from study
- Participants with Treatment-Emergent SAEs
- Participants with Treatment-Emergent SAEs leading to discontinuation from study
- Participants with Treatment-Emergent SAEs resulting in death

The following summary tables for TEAEs will be presented:

- Number and percent of participants reporting treatment-emergent AEs, grouped by MedDRA system organ class and preferred term
- Number and percent of participants reporting treatment-emergent drug-related AEs, grouped by MedDRA system organ class, and preferred term
- Number and percent of participants reporting treatment-emergent AEs, grouped by MedDRA system organ class, preferred term, and maximum severity
- Number and percent of participants reporting treatment-emergent SAEs will be tabulated by system organ class and preferred term and presented by treatment.
- Number and percent of participants reporting treatment-emergent AEs leading to study discontinuation, grouped by MedDRA system organ class and preferred term

For the summary tables above, the SOC terms and PTs will be presented in decreasing order of the total number of participants (frequency) who experienced each AE. System organ class terms and PTs with the same frequency will be presented alphabetically. In the case of multiple occurrences of the same TEAE within the same participant, each participant will only be counted once for each preferred term.

The following data listings for AEs will be provided for each participant by displaying the events captured on the CRF:

- All AEs,
- All serious AEs,
- All AEs leading to study discontinuation, and
- All AEs leading to Death.

In the AE data listings, all AEs will be displayed. AEs that are not treatment-emergent will be flagged in the AE listings.

9.2. Clinical Laboratory Evaluations

The following clinical laboratory tests will be performed during the Screening Period, Baseline (Study Day 1) pre-dose, and at all follow-up visits (Week 4, Week 16, Week 28, Week 40, and Week 52/ET/ED).

Table 3: Protocol-Required Safety Laboratory Tests

Hematology		
Erythrocytes (RBC)	Eosinophils (EOS)	Leukocytes (WBC)
Hemoglobin (HGB)	Lymphocytes (LYM)	Eosinophils/Leukocytes (EOSLE)
Hematocrit (HCT)	Monocytes (MONO)	Lymphocytes/Leukocytes (LYMLE)
Platelets (PLAT)	Neutrophils (NEUT)	Monocytes/Leukocytes (MONOLE)
Basophils (BASO)	Basophils/Leukocytes (BASOLE)	Neutrophils/Leukocytes (NEUTLE)
Serum Chemistry		
Alanine aminotransferase (ALT)	Calcium (CA)	Phosphate (PHOS)
Albumin (ALB)	Chloride (CL)	Potassium (K)
Alkaline phosphatase (ALP)	Gamma-glutamyl transferase (GGT)	Protein (PROT)
Aspartate aminotransferase (AST)	Globulin (GLOBUL)	Sodium (SODIUM)
Bicarbonate (BICARB)	Glucose (GLUC)	Urea Nitrogen (UREAN)
Bilirubin (BILI)	Creatinine (CREAT)	Urate (URATE)
	Lactate dehydrogenase (LDH)	
Urinalysis*		
Color (COLOR)	Leukocyte esterase (LEUKASE)	Protein (PROT)
Glucose (GLUC)	Nitrite (NITRITE)	Specific gravity (SPGRAV)
Ketones (KETONES)	pH (PH)	Occult Blood (OCCBLD)

* A “reflex” microscopic examination will be performed if protein, occult blood, nitrites, or leukocyte esterase is present on the basic analysis.

Screening Period: During the Screening Period only, bloods will be drawn for TSH, free T4, Vitamin B12, HepBsAg, HCV-Ab, HbA1C (diabetic participants only) and plasma P-tau181 or P-tau217 (Note – plasma collection for P-tau181 or P-tau217 not required if participant has documented evidence of AD pathophysiology prior to screening). Urine to screen for drugs of abuse (amphetamines, cocaine, opiates and phencyclidine) will also be collected during the Screening Period.

All hematology, chemistry, and urinalysis laboratory results will be presented in SI units, if available. Only laboratory parameters in the [Table 3](#), will be tabulated.

The observed values and changes from baseline of all quantitative safety laboratory results for clinical chemistry, hematology, and urinalysis (only for pH and Specific Gravity results) will be summarized using descriptive statistics showing the number of observations (n), mean (SD), median, minimum, and maximum value. A separate summary table with the number and percentage of participants for each categorical urinalysis parameter (glucose, protein, occult blood, ketone, nitrite, and leukocyte esterase) will be provided.

Baseline values for all clinical chemistry, hematology, and urinalysis parameters will be categorized as being below the normal range (Low), within the normal range (Normal), and above the normal range (High). Shift from baseline tables will present the number and percentage of participants who have observations that are Normal, Low, or High when such range characterizations are available. Shift tables will be presented for values shifting from Baseline (Study Day 1) to the Week 52/ET/ED.

Listings of all observed chemistry, hematology, and urinalysis laboratory data will be provided. Laboratory results outside the normal range will be flagged. The abnormal values will be flagged with 'L' (low) for values below the lower limit of the laboratory's normal range or 'H' (high) for values above the upper limit of the laboratory's normal range. Abnormal values will be graded as not clinically significant (NCS) or clinically significant (CS).

Abnormal results from the microscopic examination will be listed. All other laboratory assessments will only be listed.

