10. ADVERSE EVENTS/SERIOUS ADVERSE EVENTS

10.1. ADVERSE EVENTS - DEFINITION

An Adverse Event (AE) is any undesirable event that occurs to a subject during a study, whether or not that event is considered related to Study Drug. Monitoring for AEs will start after informed consent has been obtained. Examples include:

- Any treatment-emergent signs and symptoms (events that are marked by a change from the subject's baseline/entry status [e.g., an increase in severity or frequency of pre-existing abnormality or disorder])
- All reactions from Study Drug, an overdose, abuse of drug, withdrawal phenomena, sensitivity or toxicity to Study Drug
- Apparently unrelated illnesses
- Injury or accidents (Note: if a medical condition is known to have caused the injury or accident, the medical condition and the accident should be reported as two separate medical events [e.g., for a fall secondary to dizziness, both "dizziness" and "fall" should be recorded separately])
- Extensions or exacerbations of symptoms, subjective subject-reported events, new clinically significant abnormalities in clinical laboratory, physiological testing or physical examination

All AEs, whether or not related to Study Drug, must be fully documented on the AE page of the CRF and in the subject's clinical chart. Adverse events reported during the screening period or AEs secondary to study-related procedures should always be captured as not having a reasonable possibility the AE was caused by the Study Drug. Unexpected, abnormal laboratory results observed during the Screening Period should be captured as Medical History and not as an AE.

In the event that a subject is withdrawn from the study because of an AE, it must be recorded on the CRF as such. The subject should be followed and treated by the Investigator until the abnormal parameter or symptom has resolved or stabilized.

The Investigator must report all directly observed AEs and all spontaneously reported AEs. The Investigator will ask the subject a non-specific question (e.g., "Have you noticed anything different since your dose of the study medication?") to assess whether any AEs have been experienced since the last assessment. AEs will be identified and documented in the Electronic Data Capture (EDC) system in appropriate medical terminology. The severity and the relationship to the Study Drug will be determined and reported in EDC (see below).

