3.2.2. Safety Endpoints

The safety endpoints of this study include the following:

- Incidence of adverse events (AEs) including treatment-emergent, serious, related to study drug, and leading to withdrawal along with AEs by severity and relationship to study drug
- Mean change in clinical laboratory values from baseline to Weeks 4, 16, 28, 40, and 52
Shifts in the normality of clinical laboratory values from baseline to Weeks 4, 16, 28, 40, and 52
- Mean change in vital signs (blood pressure [supine], temperature, pulse rate) from baseline to Weeks 4, 16, 28, 40, and 52
- Mean change in body weight from baseline to Weeks 4, 16, 28, 40, and 52
- Shifts in physical exam (PE) findings from baseline to Weeks 4, 16, 28, 40, and 52
- Shifts in neurological exam (NE) findings from baseline to Weeks 4, 16, 28, 40, and 52
- Mean change in ECG parameters from baseline to Weeks 4, 28, and 52
- Concomitant medications/treatments usage
- Shifts in the C-SSRS from baseline to Weeks 4, 16, 28, 40, and 52.

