This study is considered a registration study. Statistical tests will be regarded as formal tests of specific hypotheses.

The data from nominal/scheduled protocol clinic visits will be included in visit-based summary tables. Unscheduled assessments, if they occur, and the ET visit data will be mapped to scheduled assessments according to the visit windows defined in section 6.1.5 for all safety and efficacy analyses. See Section 6.1.4 and 6.1.5 of this SAP for more details.

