8.8. Pooling With Other Studies

Pending the outcomes of individual studies, data from Protocol PTI-125-07 may be pooled with data from Protocol PTI-125-06. These pooled analyses will include data from weeks 0 – 52 from Protocol PTI-125-06 to match the duration of Protocol PTI-125-07. Objectives and estimands for the pooled data will mirror those in Protocol PTI-125-07. Analyses will also be similar but will include an additional categorical fixed effect of study.

9. Safety and Tolerability Analysis

All safety analyses will be performed on the safety analysis set.

Safety measures including AEs, clinical laboratory values, physical examination findings, neurologic examination findings, vital signs, ECGs, and concomitant medication usage will be summarized descriptively. No inferential statistical tests will be performed, unless otherwise specified. For quantitative variables, descriptive statistics including number of observations, mean, median, standard deviation, minimum, and maximum will be presented for observed and change from baseline values at each study visit. Qualitative variables will be summarized using counts and percentages.

For all safety and tolerability analyses, participants will be analyzed by the actual treatment and dose received and, if applicable, overall.

All safety and tolerability data will be presented in participant listings.

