9.2.1. Stopping Criteria

Potential discontinuation of study drug for abnormal liver function tests should be considered if the study participant meets one or more of the following liver chemistry threshold stopping criteria:

- ALT or AST \geq 4x ULN;
- ALT or AST \geq 3x ULN and total bilirubin \geq 2x ULN;
- ALT or AST \geq 3x ULN if associated with the appearance or worsening of fatigue, nausea, vomiting, right upper quadrant pain or tenderness, fever, rash and/or eosinophilia;

or

- ALP elevations, if deemed of liver origin and drug-related as follows:
 - ALP > 3x ULN;
 - ALP > 2.5x ULN and total bilirubin > 2x ULN; or
 - ALP > 2.5x ULN if associated with the appearance or worsening of fatigue, nausea, vomiting, right upper quadrant pain or tenderness, fever, rash and/or eosinophilia,

where ULN = Upper Limit of Normal.

Study drug should be discontinued if a participant: (1) positively affirms suicidal ideation in response to questions number 4 or 5 in the suicidal ideation section of the C-SSRS, or (2) reports any suicidal behavior or non-suicidal self-injurious behavior since their last visit in response to the C-SSRS Suicidal Behavior questions.

Bodyweight loss (compared to weight at Baseline Visit [Study Day 1]) of \geq 2 kg resulting in a BMI < 18.5 is an additional stopping criterion.

Individual results of stopping criteria will be listed and summarized by presenting the number and percentage of participants who meet at least one post-dose stopping criteria.

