14.3.5 Laboratory Data Summary Tables		
14.3.5.1.1	Safety	Summary of Laboratory Results - Serum Chemistry
14.3.5.1.2	Safety	Summary of Shift from Baseline in Serum Chemistry Results
14.3.5.2.1	Safety	Summary of Laboratory Results-Hematology
14.3.5.2.2	Safety	Summary of Shift from Baseline in Hematology Results
14.3.5.3.1	Safety	Summary of Laboratory Results -Urinalysis
14.3.5.3.2	Safety	Summary of Categorical Urinalysis Results
14.3.5.4	Safety	Summary of Stopping Criteria by Treatment

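### SAP 9.2 plans laboratory shift tables to Week 52/ET/ED alone, although SAP 3.2.2 defines the shift endpoint at five visits; SAP 11.1.1 also omits Week 28 from its creatinine and eGFR visits

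*SAP*

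**What the plan says.** SAP 3.2.2 (Safety Endpoints) includes "Shifts in the normality of clinical laboratory values from baseline to Weeks 4, 16, 28, 40, and 52". SAP 9.2 classifies each value as Low, Normal or High where a range is available, and then states the output: "Shift tables will be presented for values shifting from Baseline (Study Day 1) to the Week 52/ET/ED". The laboratory section of Table 7 in SAP 13.3 has one shift table for chemistry and one for hematology. Their titles, such as "Summary of Shift from Baseline in Serum Chemistry Results", name no visit.

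On early termination, SAP 4.2 states that "ET visit data will be mapped to scheduled assessments according to the visit windows defined in section 6.1.5 for all safety and efficacy analyses". SAP 6.1.5 repeats the rule for safety summaries and gives the windows in Table 2.1.

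On renal function, SAP 11.1.1 names Day 1 and Weeks 4, 16, 40 and 52 as the creatinine collection visits and calculates eGFR at those visits. SAP 9.2, the SAP schedule (Table 1) and protocol 7.1.5 and 7.2.1 all place clinical laboratory tests at Week 28 as well, and creatinine is in the chemistry panel.

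**The concern.** A safety endpoint is defined at five visits and the section that turns it into output names one. A programmer who follows 9.2 will not produce the endpoint at Weeks 4, 16, 28 and 40. Nothing marks this as a deliberate narrowing; SAP 10 records no change from the planned analysis.

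The window rule adds to the loss. The single planned time point describes only participants with a laboratory value in the Week 52 window. Those who left earlier are absent from it, and early leavers are a group in whom laboratory abnormalities deserve a by-arm count. Protocol 2.2 reports liver findings in the six-month rat study with raised alkaline phosphatase and bilirubin, so categorical laboratory change during treatment has some relevance to this drug.

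The Week 28 omission is smaller. It gives a wrong account of when creatinine is collected, and the eGFR visit list rests on that account.

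**Working it through.** No power, error rate or effect size is involved. The check compares visit lists and applies the SAP's own windows.

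**Shift visits**
- Defined in SAP 3.2.2: {4, 16, 28, 40, 52}, 5 visits.
- Planned in SAP 9.2: {52}, 1 visit.
- Difference: {4, 16, 28, 40}; 5 − 1 = 4 visits without a planned shift table.
- The Table 7 titles name no visit, so they do not fill the gap.

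**Where early termination values go**
- Table 2.1 target days: Week 40 = Day 281, Week 52 = Day 365.
- SAP 6.1.5 splits the interval at its mid-point: (281 + 365)/2 = 323.
- This agrees with the printed windows: Week 40 = Days 240 to 323, Week 52 = Days 324 to 407.
- Illustration: an ET sample on Day 200 falls in Days 156 to 239 and is analysed as Week 28. An ET sample on Day 300 is analysed as Week 40. Neither enters a shift table confined to Week 52, whether or not the value has returned to normal.

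**What else would show an abnormality at Weeks 4 to 40**
- Protocol 10.1 gives "new clinically significant abnormalities in clinical laboratory, physiological testing or physical examination" among its examples of adverse events, so these reach the by-arm TEAE tables.
- SAP 9.2.1 summarises the "number and percentage of participants who meet at least one post-dose stopping criteria". Not every raised liver value qualifies. The ALP criteria apply only if the rise is judged to be of liver origin and drug-related. ALT or AST from 3x to below 4x ULN needs either raised bilirubin or symptoms.
- SAP 9 states for quantitative variables that "minimum, and maximum will be presented for observed and change from baseline values at each study visit".
- SAP 9.2 flags out-of-range values in listings.
- What remains without a by-arm count is an out-of-range value outside the Week 52 window that is not recorded as an adverse event and does not meet a stopping criterion.

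**eGFR visits**
- Post-baseline chemistry collections (SAP 9.2 and Table 1): {4, 16, 28, 40, 52}.
- Listed in SAP 11.1.1: {4, 16, 40, 52}.
- Difference: {28}, 1 of 5.
- Table 7 plans the creatinine and eGFR tables by visit, and Table 9 plans the change plots at every post-baseline visit. Both imply Week 28.

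**The case against.** SAP 9.2 does not use the word only, and the table titles leave the visits open. That is true, but Week 52/ET/ED is the sole time point the section gives, and elsewhere the SAP lists visits when it means several.

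A reader might infer that Week 52/ET/ED means the last on-study value. Early leavers would then be counted, and only abnormalities that had resolved by the last visit would be missed. The documents do not support this. The same label heads the final column of the schedule and recurs for vital signs, ECGs and examinations. SAP 4.2 and 6.1.5 assign ET data by window for all safety analyses, and no last-value rule for laboratory data is given.

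A reader might also infer more serious failings, which do not stand:
- **A protocol commitment is broken.** Protocol 11.4 promises descriptive summaries of laboratory change, not shift tables. The conflict lies within the SAP.
- **Week 28 eGFR will be lost.** SAP 11.1.1 ties eGFR to the visits where creatinine is collected, and creatinine is collected at Week 28. This is a slip in a list; the visit could be dropped, but nothing instructs it.
- **A urinalysis shift table is missing.** SAP 9.2 limits shifts to parameters with range characterisations and plans a separate categorical urinalysis table. The documents do not show which urinalysis parameters have Low and High limits, so a substantive gap is not established.

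It is also fair to say that amending 3.2.2 to Week 52 would remove the mismatch. It would do so by giving up four visits and leaving early leavers out.

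**Conclusion.** The inconsistency is real and minor. As written, SAP 9.2 delivers the laboratory shift endpoint at one of five visits, and participants without a laboratory value from Day 324 onward do not appear at that visit. SAP 11.1.1 misstates one of five post-baseline creatinine visits.

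This rests on reading 9.2 as giving its full list of shift time points, and on the windows in 4.2 and 6.1.5 applying to laboratory data as they say. The documents give neither the timing of withdrawals nor the rate of out-of-range values, so no number of participants is claimed. A reader might conclude that a safety signal would be hidden. The adverse event tables, stopping-criteria summary, by-visit minimum and maximum values and flagged listings do not support that. No efficacy result or error rate is touched.

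**What to change.** In SAP 9.2, present chemistry and hematology shifts from baseline to each of Weeks 4, 16, 28, 40 and 52, with ET and unscheduled values assigned by the 6.1.5 windows. Do the same for urinalysis parameters only where normal ranges exist. Name the visits in the corresponding Table 7 titles. This delivers the endpoint in 3.2.2 and counts early leavers by arm at the visit to which their last sample maps. In SAP 11.1.1, add Week 28 to the creatinine and eGFR visits.

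All the data are already collected. The cost is a few lines of SAP text and some additional table pages.

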9.2.1. Stopping Criteria

Potential discontinuation of study drug for abnormal liver function tests should be considered if the study participant meets one or more of the following liver chemistry threshold stopping criteria:

- ALT or AST \geq 4x ULN;
- ALT or AST \geq 3x ULN and total bilirubin \geq 2x ULN;
- ALT or AST \geq 3x ULN if associated with the appearance or worsening of fatigue, nausea, vomiting, right upper quadrant pain or tenderness, fever, rash and/or eosinophilia;

or

- ALP elevations, if deemed of liver origin and drug-related as follows:
 - ALP > 3x ULN;
 - ALP > 2.5x ULN and total bilirubin > 2x ULN; or
 - ALP > 2.5x ULN if associated with the appearance or worsening of fatigue, nausea, vomiting, right upper quadrant pain or tenderness, fever, rash and/or eosinophilia,

where ULN = Upper Limit of Normal.

Study drug should be discontinued if a participant: (1) positively affirms suicidal ideation in response to questions number 4 or 5 in the suicidal ideation section of the C-SSRS, or (2) reports any suicidal behavior or non-suicidal self-injurious behavior since their last visit in response to the C-SSRS Suicidal Behavior questions.

Bodyweight loss (compared to weight at Baseline Visit [Study Day 1]) of \geq 2 kg resulting in a BMI < 18.5 is an additional stopping criterion.

Individual results of stopping criteria will be listed and summarized by presenting the number and percentage of participants who meet at least one post-dose stopping criteria.

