Simufilam was tested in single dose and repeat dose oral toxicity studies of up to 6 months in rats and 9 months in dogs. A 6-month repeat dose oral toxicity study in rats (PTI-125-NC-049) used the same doses as a 28-day study (50, 500 and 1000 mg/kg/day), which found 500 mg/kg/day to be the no-adverse-effect-level (NOAEL). In the 6-month study, the toxicological response was characterized by decreased body weights and adverse structural and functional alterations in the liver of 500 and 1000 mg/kg/day animals, including increased hepatic weight, hepatocellular hypertrophy and vacuolation, single/multiple basophilic/ eosinophilic/clear cell focus, hepatocellular degeneration, pigmentation, and oval cell hyperplasia. The presence of bile pigment was consistent with cholestasis. These findings correlated with changes to the clinical chemistry profile, including increased ALP and total/direct bilirubin. Over the 1-month recovery period, there was complete recovery of the hepatocellular degeneration and partial recovery of hepatocellular hypertrophy; other microscopic findings in the liver remained. The NOAEL in this 6-month study was 50 mg/kg/day (equivalent to 300 mg/m²), corresponding to a safety margin of 6- and 1.6-fold based on C_{max} and AUC over the 100 mg b.i.d. dose in human subjects. A second 6-month repeat dose oral toxicity study in rats determined the 6-month NOAEL in the rat to be < 125 mg/kg/day, based on hepatocellular vacuolation in both sexes and hepatocellular hypertrophy in females at 125 and 250 mg/kg.

In a 9-month toxicity study in dogs (PTI-125-NC-050), the no-effect-level (NOEL) of simufilam was 25 mg/kg. The high dose of 200 mg/kg/day was decreased to 150 mg/kg/day after 1 month due to bodyweight loss considered unsustainable for 9 months. Clinical signs were slight hypoactivity and incidences of slight muscle fasciculations early in the study, and salivation. There were no pathology findings, but the high dose was considered adverse due to two unexplained deaths. The 75 mg/kg/day NOAEL (equivalent to 1500 mg/m²) provides 38- and 19-fold safety margins based on C_{max} and AUC over the 100 mg b.i.d. dose in subjects.

[figure not shown]
Simufilam showed no mutagenic or clastogenic responses in a standard battery of genotoxicity assays.

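### The only planned by-arm count of liver chemistry by multiples of ULN filters ALP by attribution and is specified only as a total merged with suicidality and weight criteria

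*SAP*

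**What the plan says.** SAP 9.2.1 repeats the stopping criteria of Protocol 7.1.10. The ALT/AST criteria rest on the laboratory values, with bilirubin or symptoms where stated. All three ALP criteria stand under one condition: "ALP elevations, if deemed of liver origin and drug-related as follows". The same section adds a participant who "positively affirms suicidal ideation in response to questions number 4 or 5 in the suicidal ideation section of the C-SSRS" or reports suicidal or self-injurious behaviour. It also adds weight loss leading to a low BMI, which "is an additional stopping criterion". Results are to be listed and "summarized by presenting the number and percentage of participants who meet at least one post-dose stopping criteria". The table index has one table for this, 14.3.5.4, titled "Summary of Stopping Criteria by Treatment".

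Elsewhere in SAP 9.2, chemistry receives descriptive statistics by visit, listings and shift tables. On the last: "Shift from baseline tables will present the number and percentage of participants who have observations that are Normal, Low, or High". On timing: "Shift tables will be presented for values shifting from Baseline (Study Day 1) to the Week 52/ET/ED".

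**The concern.** A causality judgement can be sensible when an investigator is deciding whether to stop a drug. In a randomised comparison it is a filter applied before counting, and the control arm already does the work of separating drug effect from background. Here the filter falls on ALP alone among the liver tests.

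The nonclinical data give a reason to look at that marker. Protocol 2.2 reports that the 6-month rat study found liver changes with bile pigment consistent with cholestasis, and chemistry changes "including increased ALP and total/direct bilirubin". If simufilam raised ALP markedly in some participants, the planned tables offer no plain count of how many in each arm crossed a stated threshold. The one table that uses thresholds drops cases attributed elsewhere and may show only a total that also contains C-SSRS and weight cases.

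**Working it through.** The plan states no figure for this count, so there is none to reproduce. The first check is to set the planned outputs side by side.

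| Output | Attribution condition on ALP | ULN multiples | What it gives by arm |
|---|---|---|---|
| Table 14.3.5.4 (SAP 9.2.1) | Yes | Yes | Count; only the at-least-one total is specified |
| Table 14.3.5.1.1, descriptive chemistry | No | No | Per-visit maximum, not a count |
| Table 14.3.5.1.2, shifts | No | No; High is the top category | Count, baseline to Week 52/ET/ED |
| Table 14.3.1.2, TEAEs | No | No | Count by preferred term, if reported as an AE |
| Listings 16.2.8.1.1 and 16.2.8.5 | No for the former; criteria as written for the latter | Not tabulated | Individual records only |

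- **Shift tables.** ALP just above ULN and ALP above 3x ULN fall in the same cell. Under 9.2, a mid-study rise that resolves by the last visit is not seen. SAP 3.2.2 names shifts to every visit as an endpoint, but visit-wise shifts would still carry no size threshold.
- **Visit summaries.** Under SAP 6.1.5 a scheduled value displaces an unscheduled one in the same window. Under SAP 6.1.8 repeat results are not used unless the original is missing or invalid. A peak found at an extra draw can therefore drop out of the visit maximum.
- **Data source for the filter.** Protocol 10.3 and SAP 9.1.2 describe relatedness for adverse events. For laboratory values SAP 9.2 plans only low/high flags and a clinical-significance grade. Nothing says who deems an ALP value hepatic and drug-related, when, or in which field.
- **Contrast.** SAP 9.4 plans attribution-free threshold counts for QT and QTc.

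The second check separates what the filter does from what the merging does. Let N be participants per arm, p the proportion with a large ALP elevation, f the share of those judged hepatic and drug-related, and b the proportion meeting any other criterion, taken as independent and equal in both arms. The reported count is N × [1 − (1 − fp)(1 − b)].

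N = 804 / 2 = 402 (SAP 2.2, 1:1 allocation). Every rate below is an assumption chosen only to show the mechanism: p = 2.5% on drug and 0.25% on placebo.

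- No filter, no merging: 402 × 0.025 = 10.1 vs 402 × 0.0025 = 1.0; ratio 10.
- Filter only, f = 0.5: 5.0 vs 0.5; ratio still 10, absolute difference halved.
- Merging only, b = 2%: 402 × (1 − 0.975 × 0.98) = 17.9 vs 402 × (1 − 0.9975 × 0.98) = 9.0; ratio 2.0.
- Both: 402 × (1 − 0.9875 × 0.98) = 13.0 vs 402 × (1 − 0.99875 × 0.98) = 8.5; ratio 1.5.

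With the placebo rate held at 0.25%, a drug rate of 2% to 3%, f of 25% to 50% and b of 1% to 4%, the ratio with both features runs from 1.1 to 2.2. It is 8 to 12 with neither. When f is the same in both arms, the filter thins the counts and leaves the ratio alone, while merging shrinks the ratio.

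**The case against.** A reader might infer that a cholestatic signal would be hidden. The documents do not support that. All chemistry values are listed and flagged, per-visit maxima are shown, and High shifts are counted. Protocol 10.1 makes new clinically significant laboratory abnormalities adverse events, and these are tabulated by preferred term and arm without a relatedness filter. The gap is the absence of a by-arm count by size.

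A reader might also infer that the filter biases the comparison. If the judgement is made blind, it should thin both arms alike. The SAP's silence on its source makes it an ambiguity to resolve, not a demonstrated loss of cases.

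Three further points stand as limits. The shells are not in the documents, and the wording about individual results, like the table title, leaves room for one row per criterion. Mixed cases that also meet an ALT/AST criterion are counted without attribution, and DSMB outputs use separate shells. The toxicology must also be read whole. The cholestatic findings are described for rats at 500 and 1000 mg/kg/day. The 1.6-fold AUC and 6-fold Cmax margins belong to the 50 mg/kg/day NOAEL, and the 9-month dog study had no pathology findings.

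Finally, removing the attribution condition inside Table 14.3.5.4 would label participants as meeting a protocol criterion that they did not meet. That objection is sound and shapes the fix.

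**Conclusion.** The point holds as a gap in tabulation. Table 14.3.5.4 is the only planned by-arm count of liver chemistry by multiples of ULN. Its ALP rule depends on a judgement with no stated data source, and the only summary specified for it merges unrelated criteria. A predominantly cholestatic difference could be under-counted or diluted in the planned summaries.

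No magnitude can be given, because the documents contain no event rates; the figures above show direction under assumed rates and do not measure this trial. The conclusion assumes that the shells follow the SAP text. If they already carry one row per criterion, the merging concern falls away, but the ALP condition and the missing attribution-free counts remain. The change is cheap and worth making before unblinding. The protocol's stopping criteria are not in question.

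**What to change.** In SAP 9.2.1 and the table shells:

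1. Keep Table 14.3.5.4 as the count of participants meeting the protocol criteria, with one row per criterion by arm as well as the total. State who makes the ALP judgement and which data field holds it.
2. Add separately labelled rows, or a separate table, giving by-arm counts of participants whose maximum post-baseline ALP, ALT, AST and total bilirubin reaches the numeric ULN multiples already in 9.2.1, regardless of origin or attribution. Show attribution in a listing.
3. For these counts use all post-dose values, including unscheduled and repeat ones, and note the exception to SAP 6.1.5 and 6.1.8.
4. State the inequality for bilirubin, since 9.2.1 uses at-or-above 2x ULN with ALT/AST but strictly above 2x ULN with ALP.

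The cost is wording and programming on data already collected. The downside is that some non-hepatic ALP elevations, such as those from bone, are counted; randomisation balances these between arms in expectation.
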